Results of this study will quantify the effect size of the proposed intervention and inform future research designed to optimize intervention, focus examination based on the dominant pathophysiology (i.e., DM, PAD, or both), and examine efficacy in other populations (e.g., patients with trans-femoral amputation).

Specific Aim 1: The Primary Aim (PA1), on which this trial is powered, and the Primary Hypotheses (H1.1 and H1.2) are:

- a) PA1: Determine if the collaborative-care, home-based rehabilitation program improves performance-based and participant-report measures of physical function compared to standard of care for participants with dysvascular transtibial amputation.

[figure not shown]

Figure 1. Outcome factors after amputation

- b) H1.1: The rehabilitation program will result in greater improvements in the performance-based measures of the Timed Up-and-Go, 2-Minute Walk, and 5-meter Walk tests than standard of care at 12 weeks (primary end-point) and persist at 24 weeks following initiation of intervention.
- c) H1.2: The rehabilitation program will result in higher ratings of participant-reported physical function on the Prosthesis Evaluation Questionnaire – Mobility Section, Houghton Scale, and Patient-Specific Functional Scale than standard of care at 12 weeks (primary end-point) and persist at 24 weeks following initiation of intervention.

Specific Aim 2: The Secondary Aim (SA) and Hypothesis (H2) are:

- a) SA: Determine if the collaborative-care, home-based rehabilitation program improves physical activity when compared to standard of care for participants with dysvascular transtibial amputation.
- b) H2: The rehabilitation program will result in greater increases in physical activity than standard of care at 12 weeks (primary end-point) and persist at 24 weeks following initiation of intervention.

Exploratory Aims:

1. Exploratory Aim 1 (EA1) and Hypotheses (H3 & H4) are:

- a) EA1: Determine if the collaborative-care, home-based rehabilitation program influences the health self-management factors of self-efficacy for managing chronic disease, motivation for exercise, and healthcare use.
- b) While the study will likely be under-powered to find differences related to this aim, the, if trends in group differences are seen, data will provide a means for performing a statistical power analysis to determine sample size for future study. The hypothesized trends for group differences are:

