D5. Data Analysis. Data will be managed using REDCap (Research Electronic Data Capture; which is HIPAA compliant).⁶⁸ Primary analysis will be group differences in TUG times (primary outcome) at the 12-week time point. As a pilot feasibility study, data will only be analyzed for participants with sufficient intervention exposure, defined as six weeks. For participants who withdraw at or beyond six weeks of intervention, an early termination test will be performed and carried forward as the end-point. Participants who withdraw before completing six weeks will be lost to follow-up and no imputation will be performed for missing data. Attempts will be made to test all participants at 24-weeks. However, missing 24-week data will not be imputed from the 12 week measurement, as this would bias the effect following the primary end-point (i.e., it is expected that both groups would have worse 24- compared to 12-week outcomes). Group differences will be based on a linear model with TUG as the outcome and explanatory variables being primary medical diagnosis (PAD, DM, or both), rehabilitation site, treatment group, and baseline TUG. Group differences will be determined by this single test to protect against Type I error (α level: 0.05).

Secondary analyses will include differences at 12-weeks in the other outcomes (2MW, 5mW, PEQ-MS 12/5, Houghton Scale, PSFS, Activity level, number of healthcare provider visits, and number of hospital encounters) using the same method as for the primary outcome. A mixed-effects model with time as a fixed covariate across baseline, 12-, and 24-weeks will be used to evaluate long-term outcomes (24-week) and make inferences regarding the effectiveness of the intervention up to 12-weeks after intervention is complete. As with the other analyses, evaluation of the time trajectory will be conditioned on stratification variables and baseline values of the outcome measure. Also the mixed-effects model will not include data from subjects who drop prior to 6 weeks.

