The exploratory aim of identifying predictors of physical activity and disability will be analyzed by regression analysis. First, variables will be grouped into demographic/anthropometric, activity/mobility, health behaviors, physical health, amputated-limb health, contralateral-limb health, and cognitive/affective health, and healthcare use factors. A hierarchical process will be used to screen variables within each group of factors to identify the best predictors within each group. Finally, the best predictor variables from each group will be entered into a regression model to determine models containing subsets of the variables that predict the outcome, based on R^2_{adj} . The most parsimonious model will be identified by comparing the 10 best models, using partial F-tests.

D6. Sample Size Estimate. Sample size was estimated using TUG means and variances at discharge from the ongoing pilot study. In addition, literature was used to estimate long-term (> 3 months post-amputation) TUG scores for the population.^{60-62,69,70} Using 12.4 (3.9) seconds mean (SD) TUG time at rehabilitation discharge from the first 14 participants in the pilot study and 19.3 seconds as the average of TUG time reported for patients several months to years after amputation, a group difference of approximately 6.0 seconds was expected in TUG times at the 12-week time-point (primary end-point). With this group difference and an estimated SD of 6.0 (effect size = 1.0), 17 participants per group would provide 80% power to identify differences. The assumption is the EXP group will maintain or improve TUG times after the 12-week intervention and the CTL group will decline toward levels reported in the literature. A 3.4 second change in TUG represents a minimal detectable change for patients with lower limb amputation.⁶⁹

The goal is to enroll 44 participants and graduate 17 participants per group (n=34) at the 12-week test point. Based on data from the four participating hospitals, 150 patients will complete rehabilitation and achieve functional ambulation following dysvascular transtibial amputation

over the next 3 years. Based on the pilot study (Section C2), 60% of these patients are expected to meet inclusion/exclusion criteria (n = 90) and 50% of those will agree to participate (n = 45). A 20% loss to follow-up at 12 weeks (n=34) is estimated, which is twice the observed rates of studies with 12-week end-points that the PI has been involved with for other patient populations.

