Collaborative-Care Rehabilitation to Improve Functional Outcomes after Dysvascular Amputation

Statistical Analysis Plan
Version Date: 01.05.2014

Between-group differences in all outcomes at 12- and 24-week tests will be evaluated using maximum likelihood estimation in a multivariate repeated measures model. The maximum likelihood method uses all available data and provides unbiased estimates under the assumption that missing data are missing at random. The model for each outcome will be controlled for baseline value of the outcome, rehabilitation clinic site (VA/non-VA), diagnosis of DM, and diagnosis of PAD. Estimated group means and within-group mean changes over time for each outcome will be reported with 95% confidence intervals. This early phase study is powered for one endpoint; multiple secondary endpoints are reported to guide further research without adjustment for multiplicity.

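### Specific Aim 1 claims power for six measures at two time points, but only TUG at 12 weeks is powered and error-protected

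*Protocol*

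**What the plan says.** **Protocol, Section A, Specific Aim 1.** The lead-in reads "The Primary Aim (PA1), on which this trial is powered, and the Primary Hypotheses (H1.1 and H1.2) are". PA1 asks about both performance-based and participant-report function, and the synopsis words the primary aim the same way. H1.1 covers the "performance-based measures of the Timed Up-and-Go, 2-Minute Walk, and 5-meter Walk tests than standard of care". H1.2 covers the "Prosthesis Evaluation Questionnaire – Mobility Section, Houghton Scale, and Patient-Specific Functional Scale than standard of care". Both hypotheses apply "at 12 weeks (primary end-point) and persist at 24 weeks following initiation of intervention".

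**Protocol, D5.** "Primary analysis will be group differences in TUG times (primary outcome) at the 12-week time point". The 0.05 level goes to that comparison alone: "Group differences will be determined by this single test to protect against Type I error". The 2MW, 5mW, PEQ-MS, Houghton and PSFS are listed as secondary analyses, and 24-week outcomes go to a separate mixed-effects model.

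**Protocol, D6.** The calculation uses a TUG difference of 6.0 s with an SD of 6.0 s at 12 weeks and concludes that "17 participants per group would provide 80% power to identify differences". No expected difference is given for any other measure.

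**SAP.** One model is applied to all outcomes at 12 and 24 weeks. "This early phase study is powered for one endpoint", and the secondary endpoints are not adjusted for multiplicity. The endpoint is not named, and TUG does not appear in the SAP.

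**The concern.** The same five measures are primary in Section A and secondary in D5. H1.2 is called a primary hypothesis but has no primary test and no power calculation. The word powered is not casual here: for Exploratory Aim 1, Section A says the study will probably lack power, so the protocol does separate powered aims from under-powered ones and puts participant-reported function on the powered side.

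What is at stake is the claim made at the end. Suppose TUG is not significant and PEQ-MS is. Section A would let that be reported as support for a primary hypothesis of a powered aim, while D5 makes it one of several unadjusted secondary findings. An SAP that does not name its endpoint cannot settle the matter alone. Conversely, a significant TUG result says nothing directly about the participant-report half of PA1.

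**Working it through.** **Step 1. Reproduce the plan's figure.** Inputs from D5 and D6: difference 6.0 s, SD 6.0 s, so d = 6.0/6.0 = 1.0; alpha 0.05; 80% power. Assumed: two-sided test and equal allocation, neither of which is stated. For a two-sample t-test the required size solves at 16.7, so 17 per group. At n = 17 the non-centrality is d√(n/2) = √8.5 = 2.92 on 32 degrees of freedom, and power is 80.7%. A one-sided test would solve at 13.1, so the stated 17 matches a two-sided test of a single endpoint.

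**Step 2. What 17 per group means for the other measures.** The effect size detectable with 80% power is d = 0.99. Multiplied by the discharge SDs in Table 1:

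| Measure | SD | Difference needed |
|---|---|---|
| 2MW | 22.4 m | 22.2 m |
| Gait speed | 0.33 m/s | 0.33 m/s |
| PEQ-MS | 0.7 | 0.69 |
| PSFS | 1.1 | 1.09 |

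Table 1 has no Houghton row. The documents do not claim any of these differences. If a measure's true effect were d = 0.7, power for that single test would be 51%; at d = 0.5 it would be 29%.

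**Step 3. What the missing decision rule could imply.** The six measures are taken at 12 weeks, each tested at two-sided 0.05 with 17 per group. If they were independent:
- at least one false positive: 1 − 0.95^6 = 26.5%;
- all six significant when each has d = 1.0: 0.807^6 = 27.6%.

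Function measures on the same person will be correlated, and the documents give no correlations. A simulation of equicorrelated normal outcomes (100,000 runs) gives:

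| Assumed correlation | Any of six, null, two-sided | Any of six, null, favouring EXP | All six, d = 1.0 each | All three performance tests, d = 1.0 each |
|---|---|---|---|---|
| 0.3 | 24% | 12% | 40% | 58% |
| 0.5 | 21% | 10% | 48% | 62% |
| 0.7 | 17% | 8% | 57% | 67% |

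The directional column compares with a nominal 2.5%.

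**Step 4. Check whether both losses occur under one rule.** Under the any-of-six rule, power for at least one success is 96% or more over these correlations if every d = 1.0, so only the error rate suffers. Under the all-six rule, the false-positive rate cannot exceed 5%, so only power suffers.

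**The case against.** The strongest reply is that the documents already hold the confirmatory rule. D5 names one primary outcome at one time and gives the whole 0.05 to it, D6 sizes the trial on it, and the SAP, which has the same date as the protocol, openly says that one endpoint is powered and the rest are unadjusted. A reader can work out that the endpoint is TUG at 12 weeks. Within H1.1 and H1.2, 12 weeks is marked as the primary time. The study also describes itself as early phase and as a pilot. On this view Section A is loosely worded and nothing else is wrong.

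Much of that stands. A reader might infer that the primary aim has neither 80% power nor a 5% error rate. The documents do not support this, because inflated error needs an any-of-six rule, lost power needs an all-six rule, and neither is stated. A reader might also infer that the sample size or the primary test is faulty. Neither is: the single TUG comparison keeps its stated power and level. Counting twelve tests by giving 24 weeks equal standing would likewise go further than the marking of 12 weeks allows.

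The labels are what the reply does not answer. The SAP's disclosure covers secondary endpoints, while Section A calls five of those measures primary and says the aim containing them is powered.

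**Conclusion.** The point holds as an inconsistency between the aims and the analysis. The power statement in Specific Aim 1 is unsupported for five of six measures and for all of H1.2. The TUG test at 12 weeks and the 17 per group are sound (80.7% power, 5% level).

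The consequence depends on a rule that is not given. It is either a two-sided false-positive rate of about 17% to 24% (8% to 12% favouring EXP) or power of about 40% to 57%, but not both. These ranges assume equal correlations of 0.3 to 0.7, unadjusted two-sample comparisons, and, for power, d = 1.0 on every measure. That last assumption is generous, since the documents argue for such an effect only on TUG. The planned models adjust for baseline, which could raise power for any single measure but would not supply the missing rule. The correction is worth making because it changes what the trial may claim about participant-reported function.

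**What to change.** - In Specific Aim 1, limit the power statement to TUG at 12 weeks.
- Reword PA1 there, and the primary aim in the synopsis, so that the confirmatory question is TUG at 12 weeks. Saying that TUG decides PA1 while PA1 still names participant-report measures would leave the contradiction in place.
- Label 2MW, 5mW, all of H1.2 and all 24-week comparisons as secondary and unadjusted, in line with D5.
- Name TUG at 12 weeks in the SAP as the one powered endpoint.
- Optional: if a confirmatory claim of persistence is wanted, test TUG at 24 weeks only after a significant 12-week result. This leaves the primary test's power unchanged, but the correction does not depend on it.

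The cost is a few sentences in Section A, the synopsis and the SAP. Sample size, data collection and the primary test stay as they are. The sponsor can no longer call participant-reported function a primary, powered hypothesis.

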Collaborative-Care Rehabilitation to Improve Functional Outcomes after Dysvascular Amputation

Protocol Version: January 5, 2014

COMIRB Protocol

COLORADO MULTIPLE INSTITUTIONAL REVIEW BOARD
[name] [contact] [contact]

Title: Collaborative-Care Rehabilitation to Improve Functional Outcomes after Dysvascular Amputation

Principal Investigator: [name], PT, Ph.D.
V1.3

SYNOPSIS

Objectives

The objective of this study is to determine the efficacy of a collaborative-care, home-based rehabilitation program for improving functional outcomes following dysvascular transtibial amputation. The primary aim is to determine if the rehabilitation program improves performance-based and participant-report measures of physical function, compared to standard of care, for participants with dysvascular transtibial amputation. The secondary aim is to determine if the rehabilitation program improves daily physical activity, compared to standard of care, for participants with dysvascular transtibial amputation. Two exploratory aims are: 1) determine the efficacy of the intervention for promoting health self-management, measured as participant-reported self-efficacy for managing chronic disease, motivation for exercise, and health-care resource use and 2) identify factors at initial testing that are predictive of physical activity level and disability 24 weeks after intervention.

Design and Outcomes

This will be a randomized, controlled clinical trial on the effects of 12 weeks of collaborative-care, home-based rehabilitation on physical function outcomes. Outcome variables include:

1. Performance-Based Physical Function Measures:
 - a. Timed Up-and-Go (TUG)¹
 - b. Two-Minute Walk (2MW)²
 - c. Five-meter Walk (5mW)³
2. Self-Report Physical Function Measures:
 - a. Prosthesis Evaluation Questionnaire – Mobility Section (PEQ-MS)⁴
 - b. Houghton Scale⁵
 - c. Patient-Specific Functional Scale (PSFS)⁶
3. Activity Measurement:
 - a. Physical activity monitors (Actigraph) worn for 1 week following each test session (baseline, 12-week, 24-week). These monitors are valid tools for measuring relative level of activity (e.g., sedentary, light, moderate, vigorous) for various patient populations⁷⁻⁹ and are valid and reliable spatiotemporal gait measures for patients with lower limb amputation.^{10,11}
4. Self-Efficacy and Motivation:
 - a. Self-Efficacy in Managing Chronic Disease (SEMCD) questionnaire^{12,13}

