 - (1) H3: The rehabilitation program group will tend to have greater positive change in ratings on the Self-Efficacy in Managing Chronic Disease (SEMCD) questionnaire and Intrinsic Motivation Inventory (IMI) Interest and Enjoyment Subscales, compared to the standard of care group at 12 and 24 weeks following initiation of intervention.
 - (2) H4: The rehabilitation program group will tend to have higher numbers of attended healthcare provider appointments and lower numbers of hospital contacts at 12 weeks and 24 weeks, compared to the standard of care group.

2. Exploratory Aim 2 (EA2) and Hypothesis (H4) are:

- a) EA2: Identify factors predictive of physical activity level and disability measured by activity monitors and self-reported disability (World Health Organization Disability Assessment Schedule 2.0), respectively.
- b) H5: Significant predictors of physical activity and disability will be identified from the categories of demographic/anthropometric, activity/mobility, health behaviors, physical health, amputated-limb health, contralateral-limb health, cognitive/affective health, and healthcare use factors for participants at 24 weeks following intervention, regardless of group assignment.

B. Background and Significance

B1. Significance. Limitations in physical function are common following dysvascular major lower limb amputation.^{28,29,31} This is a significant issue considering that dysvascular amputation is becoming increasingly more common in the United States. Dysvascular amputation is operationally defined as amputation resulting from severe PAD with critical limb ischemia or severe DM with dense distal sensory and motor neuropathy leading to a non-healing wound (or a combination of these two related, but separate pathophysiologies). The projection of 2.3 million people living with amputation in the United States by the year 2050 represents an increase of nearly 100% from current values.¹⁹ As a result, dysvascular amputation has become a major healthcare issue in the U.S, including an economic problem.³²

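### The exploratory 24-week predictor model specifies no treatment-group term, although the trial hypothesises a lasting treatment effect on one of its two outcomes

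*Protocol*

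**What the plan says.** The protocol synopsis sets the second exploratory aim as to "identify factors at initial testing that are predictive of physical activity level and disability 24 weeks after intervention". Exploratory Aim 2 names the two outcomes: activity from the monitors and self-reported disability on the WHODAS 2.0. H5 then looks for predictors "for participants at 24 weeks following intervention, regardless of group assignment" and lists eight categories of factor. Treatment group is not one of them.

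The Data Analysis section (D5) repeats the list: "First, variables will be grouped into demographic/anthropometric, activity/mobility, health behaviors, physical health, amputated-limb health, contralateral-limb health, and cognitive/affective health, and healthcare use factors". Variables are screened within each category, and then "the best predictor variables from each group will be entered into a regression model to determine models containing subsets of the variables". In that sentence, group means a category of factors, not a trial arm. Selection is by adjusted R-squared and partial F-tests among the ten best models.

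Two other places bear on this. H2 (Specific Aim 2) expects "greater increases in physical activity than standard of care at 12 weeks (primary end-point) and persist at 24 weeks". The primary TUG model in D5 does name the arm, with "explanatory variables being primary medical diagnosis (PAD, DM, or both), rehabilitation site, treatment group, and baseline TUG". The SAP deals only with between-group comparisons and does not mention the predictor model.

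**The concern.** H2 and H5 concern the same variable, monitored physical activity, at the same follow-up visit. If H2 is right, arm is a randomised and fully observed source of variation in the outcome that H5 models. Nothing in the description of the predictor model accounts for it.

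Two things follow. The residual variance is larger than it needs to be, so slopes are less precise. And in the one randomisation that is realised, a baseline factor that differs between two small arms by chance absorbs part of the treatment effect. Screening and a best-subset search favour whatever looks strongest in that data set. What is at stake is the list of predictors carried forward to later studies. The primary and secondary comparisons are not affected.

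**Working it through.** **Inputs from the documents.** 17 per arm (34 in all) expected at 12 weeks, and 44 enrolled (D6). Missing 24-week values are not filled in from week 12 (D5), so fewer than 34 may be available. Eight predictor categories (H5, D5).

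**Assumptions.** The documents give neither an effect size nor an SD for activity, so d, the 24-week arm difference in within-arm SDs, is varied from 0.3 to 1.0. Tests are two-sided at 0.05. There is one normally distributed baseline predictor.

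**The plan's own figure.** D6 gives 17 per group for a TUG difference of 6.0 s with SD 6.0 (effect size 1.0) and 80% power. The exact t-test gives 78.1% power at 16 and 80.7% at 17, so 17 is reproduced. D6 gives no figure for the predictor model.

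**Precision.** With 1:1 allocation, omitting arm multiplies the residual variance by 1 + d²/4. Including arm costs one degree of freedom. For a normal predictor the expected inverse sum of squares rises from 1/(34 − 3) = 1/31 to 1/(34 − 4) = 1/30. The ratio of slope standard errors, with arm to without, is therefore about √[(31/30) / (1 + d²/4)].

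- d = 0.3: √(1.0333/1.0225) = 1.005, a loss of 0.5%
- d = 0.5: √(1.0333/1.0625) = 0.986, a gain of 1.4%
- d = 0.8: √(1.0333/1.16) = 0.944, a gain of 5.6%
- d = 1.0: √(1.0333/1.25) = 0.909, a gain of 9.1%
- Break-even: d²/4 = 1/30, so d = 0.37

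**Power and false positives.** Simulation with 60,000 runs per setting, 17 per arm. Power is for a true slope of 0.5 SD per SD. The last two columns are the false-positive rate for a useless predictor, restricted to runs in which it differs between arms by at least 0.5 SD.

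| d | Power, no arm | Power, arm | False positive, no arm | False positive, arm |
|---|---|---|---|---|
| 0.3 | 76.4% | 76.2% | 5.7% | 5.2% |
| 0.5 | 75.1% | 76.4% | 6.7% | 4.9% |
| 0.8 | 71.5% | 76.3% | 9.3% | 5.3% |
| 1.0 | 68.4% | 76.2% | 11.1% | 5.0% |

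In the imbalanced runs the useless predictor has a mean spurious slope of 0.08 (d = 0.5) to 0.16 (d = 1.0) without arm, and about 0 with it. Over all runs, its false-positive rate without arm stays at 4.9% to 5.1%.

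**How often such an imbalance arises.** The standard error of a baseline difference is √(2/17) = 0.343 SD. A difference of at least 0.5 SD is 0.5/0.343 = 1.46 standard errors, with two-sided probability 14.5%. For eight independent predictors, one per category, the chance that at least one is so imbalanced is 1 − (1 − 0.145)⁸ = 71%.

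**Other sample sizes.** For d from 0.5 to 1.0, the conditional false-positive rate without arm is 6.3% to 9.6% at 14 per arm and 7.4% to 12.0% at 22 per arm. The picture does not change.

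**The case against.** The strongest reply is that the documents are silent rather than wrong. The phrase about group assignment can be read as saying who is analysed and to whom the predictors apply, and D5 does not forbid an arm term. This stands in part. A reader might infer that the sponsor decided to exclude arm, but no text says so; the absence is inferred from an explicit list of categories. Still, only screened variables from those categories are said to enter the model, so followed as written it has no arm term. A main effect for arm keeps one common slope for all participants and so leaves the aim intact.

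The second reply is that randomisation already protects baseline predictors. It does on average: a reader might infer inflated type I error or systematic bias, and the simulation shows neither. Nor are lost precision and chance imbalance two separate harms. A one-standard-error imbalance shifts a slope by d × 0.25 × √(2/17), or 0.043 at d = 0.5 and 0.086 at d = 1.0. This equals √[(d²/4)/34], the extra residual variance spread over 34 participants. The conditional false-positive rates describe what that variance does in an unlucky randomisation; they do not add to it.

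Third, arm may not matter much. It explains (d²/4)/(1 + d²/4) of the variance, which is 5.9% at d = 0.5 and 20% at d = 1.0. A baseline factor correlated 0.24 or 0.45 with the outcome would explain as much, so the documents do not support calling arm the largest source of variation. The only effect size of 1.0 that they give is for TUG at 12 weeks.

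Finally, searching eight categories and ten best models on about 34 participants is probably a greater threat to these predictors than one omitted covariate. That is fair, and it is a reason to rank this point low rather than to leave it out.

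**Conclusion.** The point holds as a small, specific improvement. The predictor analysis pools the arms and specifies no arm term, while H2 expects a lasting effect on one of its two outcomes. For d between 0.5 and 1.0 the benefit of the term is a standard error lower by about 1.4% to 9%, one to eight points of power for a slope of 0.5, and protection when a predictor happens to be imbalanced. Below about d = 0.37 there is nothing to gain.

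The overlap with a named hypothesis is exact for physical activity only. WHODAS disability does not appear in H1 or H2, although section D7 lists it among the self-report function measures, so a reader should not extend the argument to it with equal force.

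The result rests on an assumed d, on predictors measured at initial testing as the synopsis says (H5 and D5 do not repeat this), and on H2 and H5 meaning the same 24-week session, the only one scheduled after week 12. The simulated rates are for one predictor tested at 0.05, not for the whole selection procedure. Because the aim is exploratory, the severity is low.

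**What to change.** In D5, state that treatment group is forced as a main effect into every predictor model, both at the within-category screening step and in the final model, before any variable is selected. Report predictor slopes adjusted for group. If the sponsor prefers to leave arm out, D5 should say so and give the reason.

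The cost is one sentence and one degree of freedom, using a variable already in the data set. If the treatment effect on activity is small, the precision loss is negligible: 0.5% of a slope's standard error at d = 0.3, and at most √(31/30) − 1 = 1.7% if there is no effect at all.

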The pilot study also examines the comorbidity profile and rehabilitation dose for patients. Data collected to this point have guided development of the proposed intervention (Table 2).

D. Research Design and Methods

Table 2. Standard of care interventions following dysvascular transtibial amputation (n = 14)

Category	Specific Interventions
Gait Training	
 •Level-ground walking •Parallel-bar walking •Community walking •Stair ascent/descent •Treadmill walking
Neuromuscular Re-education	
 • Variable techniques
Therapeutic Exercise	
 •Hip muscle strengthening •Knee muscle strengthening •CV/Endurance training •Hip stretching exercise •Knee stretching exercise •Trunk/Core strengthening
Prosthetic Don & Doff / ADL	
 •Don/doff prosthesis •Basic ADL training
Standing Balance / Pre-Gait Training	
 •Standing weight-shifts •Step-ups •Side-steps •Bilateral standing balance •Single-leg standing balance
Mobility Training	
 •Supine-sit mobility •Sit-stand mobility •Simulated community & home mobility training

Note: Specific categories listed in order of frequency during rehabilitation and specific interventions listed in order of frequency within each category.

initial test session at their home (or the research lab, whichever is more convenient for the participant) and be randomized to group: 1) experimental (EXP) or 2) control (CTL), stratified by sex.

D4. Intervention. Experimental (EXP) Group: Objectives for the collaborative-care, home-

Table 1. Physical function rehabilitation outcomes following dysvascular amputation

	Initial Exam	Discharge
TUG (s)	26.4 (15.3)	12.4 (3.9)
Gait Speed (m/s)	0.57 (0.34)	1.16 (0.33)
TMW (m)	76.8 (22.8)	125.2 (22.4)
PEQ-MS (0-4)	2.4 (1.0)	2.8 (0.7)
PSFS (0-10)	3.5 (2.0)	5.9 (1.1)

Note: TUG: Timed Up-and-Go, TMW: Two-Minute Walk, PEQ-MS: Prosthesis Evaluation Questionnaire – Mobility Section, PSFS: Patient-Specific Functional Scale

N = 14, Rehab Duration = 8.3 (5.8) weeks. All values are mean (SD).

D1. Subjects. Forty-four participants with dysvascular transtibial amputation.

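### Randomisation is stratified by sex, but the 12-week models and the SAP model leave sex out, and the protocol's reference to stratification variables is undefined

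*Protocol*

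**What the plan says.** Five statements bear on this point.

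- **Protocol D3 (randomisation):** participants are "randomized to group: 1) experimental (EXP) or 2) control (CTL), stratified by sex". No other stratification factor is named in the protocol or the SAP.
- **Protocol D5, primary analysis:** a linear model for 12-week TUG, with "explanatory variables being primary medical diagnosis (PAD, DM, or both), rehabilitation site, treatment group, and baseline TUG".
- **Protocol D5, secondary 12-week outcomes:** analysed "using the same method as for the primary outcome", so with the same covariates apart from the baseline variable.
- **Protocol D5, mixed-effects model over baseline, 12 and 24 weeks:** "As with the other analyses, evaluation of the time trajectory will be conditioned on stratification variables and baseline values of the outcome measure". The variables are not listed.
- **SAP:** one repeated measures model for every outcome at 12 and 24 weeks, "controlled for baseline value of the outcome, rehabilitation clinic site (VA/non-VA), diagnosis of DM, and diagnosis of PAD".

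Protocol D6 sizes the trial to "graduate 17 participants per group (n=34) at the 12-week test point".

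**The concern.** Stratifying balances sex between the arms. An analysis that ignores sex leaves any sex-related variation in the error term, although the design has removed it from the comparison between arms. The reported standard error is then larger than the true one. The test rejects too rarely under the null and loses some power under the alternative. D6 leaves little room for that, since 17 per group only just reaches 80%.

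There is also a problem of specification. The D5 mixed model can be read as including sex, while the SAP model, which covers the same 24-week question, has a fixed list without it. Someone following D5 and someone following the SAP could fit different covariates, and for the D5 mixed model the choice could be made after outcomes are seen.

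**Working it through.** **1. Compare the texts.** Suppose the stratification variables in D5 are those used at randomisation. By D3 that means sex. Then the phrase saying this is done as in the other analyses is false, because the primary list does not contain sex. Suppose instead they are diagnosis and site, which do appear in the primary list. Then either D3 omits two randomisation factors, or the term is loosely used for covariates. The SAP carries the same date as the protocol and does not settle it.

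**2. Reproduce the plan's own figure.** Inputs from D6 are a difference of 6.0 s and SD 6.0, so effect size 1.0. Alpha is 0.05 from D5 (two-sided assumed). The two-sample t-test needs 16.7 per group, rounded up to 17. Power is 80.7% at 17 and 78.1% at 16. The D6 figure of 17 per group is reproduced.

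**3. Effect on the standard error.** Assume 17 per arm, balanced within sex, a proportion p of men, and a sex effect of d residual SDs. The documents give neither p nor d. Without sex, the expected residual mean square relative to the true residual variance is

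(32 + 34·p(1−p)·d²) / 32.

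The square root gives the overstatement of the standard error:

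| Men/women per arm | p(1−p) | d = 0.5 | d = 1.0 |
|---|---|---|---|
| 9/8 (53% men) | 0.249 | √(34.12/32) = 1.033 | √(40.47/32) = 1.125 |
| 12/5 (71% men) | 0.208 | √(33.76/32) = 1.027 | √(39.06/32) = 1.105 |

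Sex then explains p(1−p)d² / (1 + p(1−p)d²) of the variance: about 5–6% at d = 0.5 and 17–20% at d = 1.0.

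**4. Effect on the test.** Simulation with 40,000 runs per cell, total SD fixed at 1, treatment effect 1.0, no baseline term. Ranges cover the two sex splits.

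| Sex effect d | Power, sex omitted | Power, sex included | Type I error, sex omitted | Type I error, sex included |
|---|---|---|---|---|
| 0 | 80.7–80.9% | 80.7–80.8% | 5.0–5.2% | 5.0–5.2% |
| 0.5 | 81.0–81.2% | 82.6–82.8% | 4.2–4.6% | 4.9–5.1% |
| 1.0 | 82.6–83.1% | 87.3–88.5% | 3.0–3.2% | 5.0–5.1% |

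A separate calculation in terms of variance explained agrees. At 10%, power is about 82% omitted and 84–85% included. At 20%, it is about 83% and 88–89%.

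**5. Variations.**
- *Baseline in the model (assumed correlation 0.6), effect 0.8:* including sex gains 1.3–1.7 points at d = 0.5 and 5.1–5.8 at d = 1.0.
- *Sex acts only through baseline:* power is 79.4–79.6% omitted and 79.0–79.5% included, so there is no gain.
- *22 per arm balanced on sex, then 5 per arm lost at random:* type I error with sex omitted is 4.4–4.8% (d = 0.5) and 3.2–3.7% (d = 1.0). The power gain from including sex is 1.2–1.4 and 4.9–6.0 points.

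**6. Cost of the extra term.** With 34 completers, and assuming a four-level site term, residual degrees of freedom are 34 − (1 intercept + 1 group + 1 baseline + 2 diagnosis + 3 site) = 26. Adding sex gives 25. The critical t moves from 2.056 to 2.060, about 0.2%. If sex explains nothing, power moves from 80.1% to 80.0%, or from 80.4% to 80.2% with a two-level site term.

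**The case against.** The strongest reply is that the harm is small and the analysis without sex is valid. In the table under step 4, power with sex omitted never falls below the planned 80%, so what is lost is a gain above plan. Both documents adjust for baseline, which that table does not. With baseline in the model and the planned effect of 1.0, the loss at a sex effect of 1.0 SD was about 2 points at a baseline correlation of 0.6, 3–4 at 0.5 and 5–6 at 0.3. The correlation is itself an assumption. A 1.0 SD sex effect is large, and nothing in the documents supports it. This stands: 6 points is the top of an assumed range, and 1 to 2 points is the figure for a moderate effect.

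It can also be said that the primary D5 list and the SAP list are closed, so neither leaves sex to the analyst's discretion. That is correct for those two models. The open question is confined to the D5 mixed model, which is where the undefined term appears.

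Finally, the term may simply be loose wording for diagnosis and site. That is possible, but the text does not say so. Under that reading the one factor known to have been used at randomisation is still absent from every model.

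**Conclusion.** The concern holds. Sex is the only stratification factor named. It is missing from the D5 primary and secondary 12-week models and from the SAP model, and D5 refers to stratification variables that it does not define. The consequence is modest: no bias, no inflation of type I error, and a conservative test only if sex predicts outcome beyond baseline. Over assumed residual sex effects of 0 to 1.0 SD, the loss runs from nothing to about 6 power points, and type I error with sex omitted falls from 5% to about 3%. These sizes rest on 17 completers per arm, 53% or 71% men, and a two-sided test. The inconsistency in the text depends on none of these assumptions. The change should be made because it costs almost nothing and closes a gap between the protocol and the SAP.

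**What to change.** - In Protocol D3, state every factor actually used to stratify randomisation: sex, plus any other if D3 is incomplete.
- In Protocol D5, define the stratification variables as exactly that list.
- Add sex to the D5 primary model, and so to the secondary 12-week models, and to the SAP repeated measures model. If D3 turns out to omit a factor, add that factor too. If the sponsor prefers to leave sex out, the SAP should say so and give the reason before outcomes are seen.

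Sex is known at randomisation, so no new data are needed and the sample size does not change. The cost is one definition, one word in each covariate list and one residual degree of freedom. This edit does not reconcile the different coding of site and diagnosis in D5 and the SAP, which needs its own correction.
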